**PI: [name]**

**The University of Arizona**

**[name]**

**[name]**

**T: [contact]**

## Sample Size: 20 subjects

### Introduction:

Postoperative surgical site infection (SSI) remains a common and serious complication after emergency abdominal surgery with incidence varying between 14 to 32% (1, 2). Seamon et al in a study of 503 trauma patients who underwent laparotomies for *any* enteric injuries demonstrated that primary closure leads to a 3 fold increase in SSI rate (32.1% vs. 9.8%) and 3 fold increase in fascial dehiscence (8.6% vs. 2.6%) compared to wounds managed with delayed closure (3). In contrast, an individual undergoing major *elective* operation is expected to have a 2% risk of SSI (4). Among the various gastrointestinal sites, colorectal procedures are associated with the highest risk of SSI due to the change in bacterial flora from largely aerobic gram-positive organisms in the proximal bowel to more virulent anaerobic species in the colon and rectum such as *Escherichia coli*, *Streptococcus*, *Bacteroides fragilis*, *Proteus* and *Klebsiella* (5-8). In a prospective cohort study of 2393 patients undergoing elective colorectal surgeries, Huebner et al. has shown hospital SSI rates varying between 4% to 25.2% and individual surgeon rates varying from 3.7 to 36.1% (9-14). The most feared consequence of SSI is fascial dehiscence and necrotizing soft tissue infections, which can lead to some of the most difficult surgical complications such as large ventral hernias or enterocutaneous fistulas (15-17).

Over the years, various techniques have been employed to decrease SSI after bowel surgeries, particularly in emergent cases with significant enteric contamination. They include wet –to-dry dressing changes followed by delayed primary closure; wet-to-dry for several days, followed by VAC; or take a chance with infection with primary closure. Unfortunately, in the current age of medical practice treatment of the abdominal wound after emergent surgeries with enteric contamination is still largely “surgeon preference.” Among the previously mentioned techniques, most employ some form of wet-to-dry dressing change (18-19). A systematic review of 8 clinical trials encompassing 623 patients with contaminated abdominal wounds randomized to wet-to-dry dressings or delayed primary closure did not provide definitive evidence that there is advantage of one over the other in reducing surgical site infections (20). Either method involves the patient having an open wound for some time that is resource intensive and costly to manage, not to mention traumatic for the patient (21).

The VAC has revolutionized the management of complicated wounds. It operates on the principles of applying constant negative pressure therapy to a wound bed through a porous sponge to stimulate local blood flow, decrease interstitial edema and remove harmful enzymes in order to promote healing (22-25). However, the immediate application of the VAC after emergent highly contaminated operations has not been studied. Anecdotally, surgeons are reluctant to immediately use the VAC because theoretically the local environment after VAC closure is similar to primary closure. Some surgeons, however, will use the VAC after an initial 3 to 4 days of wet-to-dry, when the wound is heavily infiltrated with host neutrophil activity. This is a common approach at our institution. However, patients without insurance coverage cannot benefit from this technique, and often have to resort to the cumbersome and painful wet-to-dry dressing changes. A technique utilizing existing technology that can achieve definitive wound closure before the patient is discharged home is desperately needed. The VeraFlo, we believe, is that solution.

The Vacuum-Assisted Closure (V.A.C.) VeraFlo System (Kinetic Concepts, Inc., San Antonio, TX) combines the original VAC with a fluid infusion system into the wound bed. A calculated amount of bactericidal solutions such as Dakin’s solution can be infused into a contaminated wound, bathe the wound for predetermined intervals, then removed via the proven mechanics of the VAC system. The VAC system has been shown to be suitable for complicated wounds resulting from trauma and infection (22-27). It has also been theorized that contrary to the wet-to-dry technique, VAC instillation therapy allows distribution of the irrigant evenly over the entire wound bed. Various solutions have been utilized for infusion, including Normal Saline and Dakin’s Solution up to ¼ strength.

Dakin's solution, or sodium hypochlorite (NaOCl), has been shown to be bactericidal to organisms commonly associated with surgical wound infections such as *Enterococcus* species, *Bacteroides fragilis*, and *E. coli*. 0.125% Dakin's solution is commonly used for daily wet-to-dry dressing changes in chronic wounds (28-29). Exposure of the above mentioned virulent bacterial cultures inoculated onto agar plates for 30 minutes at the standard concentration of 0.25% and 0.025% of Dakin's solution proved it to be bactericidal against all organisms. Additionally, animal studies showed no difference between the Dakin's solution at this dilution and Normal Saline controls in *in vivo* toxicity on fibroblasts. The concern of using the VAC immediately on highly contaminated wounds due to bacterial proliferation is now mitigated by the addition of the bactericidal instillation therapy.

We propose using the VeraFlo with Dakin's solution for the first 3 postoperative days, followed by delayed primary closure on postoperative day 4. We believe this technique can achieve earlier wound closure, decrease patient discomfort, improve cost savings, and potentially standardize and revolutionize our management of heavily contaminated wounds.

### **Clinical Hypotheses:**

We hypothesize that immediately after emergent operations involving enteric injuries e.g. traumatic injuries involving stomach, small bowel, or colon; or the non-trauma emergent general surgical pathologies involving the above hollow viscera, the application of VeraFlo with 1/4% Dakin's solution for 3 days, followed by delayed primary closure on postoperative day 4, will be associated with a low risk of wound infection, achieve more expedient wound closure, ease nursing care and increase patient comfort compared to the current common practice of wet-to-dry dressing changes.

### **Primary Outcome:**

The primary outcome of the study will be the rate of superficial and deep incisional surgical site infection, as defined by the Center for Disease Control and Prevention (CDC) definitions. (30).

#### **Superficial incisional SSI**

Must meet the following criteria:

Infection occurs within 30 days after any NHSN operative procedure (where day 1 = the procedure date), including those coded as 'OTH'\*

and

involves only skin and subcutaneous tissue of the incision

and

patient has at least one of the following:

- a. purulent drainage from the superficial incision.
- b. organisms isolated from an aseptically-obtained culture of fluid or tissue from the superficial incision.
- c. superficial incision that is deliberately opened by a surgeon, attending physician or other designee and is culture positive or not cultured

and

patient has at least one of the following signs or symptoms: pain or tenderness; localized swelling; redness; or heat. A culture negative finding does not meet this criterion.

- d. diagnosis of a superficial incisional SSI by the surgeon or attending physician or other designee .

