#### **B. Safety Endpoint(s):** wound infection and adverse reaction to Dakin's Solution.

#### **Design:**

A.  Basic Science (Bench or Laboratory)	 Pre-Clinical (Animal)	 Clinical (Human) X
B.  Care Report	 Registry	 Study (Trial) X
C.  Retrospective	 Prospective X	
D.  Non-randomized X	 Randomized	
E.  No Control or Sham	 Sham-controlled	 Reference-controlled X
F.  Single-arm X	 Multiple-arms - Specify (#): _____	
G.  Single-center X	 Multiple-centers - Specify (#): _____	

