### **Subject Exclusion Criteria**

Prisoners

Age<18

Pregnancy

Patients with allergy to Dakin's (sodium hypochlorite) solution

Enrolled in a concurrent ongoing interventional, randomized clinical trial.

This prospectively collected cohort of patients will be compared to the similar historical cohort from 2008-2013. We will review medical charts of the patients admitted to UAMC following the same inclusion and exclusion criteria described above to perform a retrospective review. We will collect the same data points as in prospective cohort.

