### **Recruitment Methods and Consenting Process:**

The attending trauma surgeon will identify eligible patients for the prospective cohort. Recruitment and consent will happen in person with a thorough explanation of the treatment protocol by the PI, trauma surgeons, research coordinator or a research fellow. Patients or their Legal Authorized Representatives (LAR) will be informed about the study and consented. Should the patient or the LAR decline participation in the study, immediate cessation of data collection will take place and their information will not be included in the final data analysis.

Retrospective cohort of patients will be identified through medical chart review and we request waiver of consent for this patient population under 45 CFR 46.116(d) and 21 CFR 50.55 (d) as this retrospective research involves no more than minimal risk to subjects, doesn't alter the treatment or management in anyway as it had

already been completed, and it could not practicably be carried out without the waiver as those patients have completed their treatment and it would be extremely hard to obtain consent.

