### **Procedures Involved in the Human Research:**

We will approach patients upon the diagnosis to consent them for this prospective study. During the process, the details of the trial will be reviewed along with potential risks and benefits, the endpoints of interest and the process by which these endpoints are evaluated. When notified of trial enrollment, the patient or their legal representative will be given the opportunity to withdraw from further data and sample collection. Those who consent will be enrolled to collect data on outcomes, baseline parameters and follow-up period to evaluate efficacy of VeraFlo for management of contaminated abdominal wounds after emergent surgery. VAC with 1/4% Dakin's solution will be placed immediately at the end of the surgery for the first 3 postoperative days, followed by delayed primary closure on postoperative day 4. Wound will be swabbed at the end of surgery before placing the VAC and before skin closure on Day 4. All follow-ups will be performed as a standard of care.

Data collected will include the following: demographics (i.e. BMI), hemodynamic parameters at the time of presentation and operation, source of infection, imaging studies outcomes, lab tests, surgical procedure performed and its duration, vasopressors, estimated blood loss and transfusion records, antibiotics used and duration, comorbidities (Charlson Morbidity Index, APACHE II), trauma registry data, and complications (if any) during their hospital stay and follow-up in clinic, length of stay (in ICU and in hospital), intra-abdominal wound culture, wound closure details, pain level, cost, wound appearance (recorded by photograph), wound culture, infection, time of nursing care.

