#### **Statistical Analysis:**

#### **Sample Size Calculation:**

- A. Event Rate Assumption(s): <5%
- B. Study Group (%): 100%
- C.  Comparator or  Sham Group (%): historic cohort from previous 3 years.
- D. Power Estimation:  95%  90%  85%  80% or Other – Specify: \_\_\_\_%
- E. Evaluable Rate Consideration: Specify: \_\_\_\_%
- F. Sample Size Calculation: 20 Total Number of Subjects. When population is not divided evenly, please specify how it will be divided and rationale for doing so:
- G. Interim Analysis - Sample Size Re-calculation:  Yes  No  Specify rationale:
- H. Number of Centers Projected: 1

This is an observational prospective study with no concurrent arm for comparison; we will use historic data from our center over the last 3 years to analyze results. The advantage of this approach is that there was no change in medical providers among trauma surgeons in the last 3 years. We also have a robust prospectively collected trauma registry that allows performing this analysis. We will identify patients who have undergone emergent abdominal surgery with hollow viscus violations, and had undergone wet-to-dry dressing changes. A Propensity matching analysis will be performed to match patients from the historic cohort to the current patients by demographics, disease severity and laboratory tests. A univariate analysis, independent t-test, and a Kaplan-Meier survival analysis will be performed to compare rate of infection, time-to-closure, and cost analysis.

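### SSI is observed prospectively and unmasked in the VeraFlo cohort but read from past charts in the controls, with no common rule for classifying it

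*Combined protocol and SAP*

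**What the plan says.** The Design section marks the trial as "Non-randomized X" and single-arm. The Sample Size Calculation section adds: "This is an observational prospective study with no concurrent arm for comparison". The primary outcome is "the rate of superficial and deep incisional surgical site infection", using CDC definitions.

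Under Superficial incisional SSI, once timing and depth are met, it is enough that the "patient has at least one of the following". Criterion b is a positive culture obtained aseptically. Criterion d is "diagnosis of a superficial incisional SSI by the surgeon or attending physician or other designee", with no sign, culture or second reader required. The deep incisional definition has no equivalent of criterion d.

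For the VeraFlo cohort, Recruitment Methods states: "The attending trauma surgeon will identify eligible patients for the prospective cohort". Procedures Involved in the Human Research schedules two wound swabs, one at the end of surgery and one before skin closure on day 4. Its list of data to collect ends with "wound appearance (recorded by photograph), wound culture, infection, time of nursing care".

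For the controls, the historical-cohort paragraph under Subject Exclusion Criteria says: "We will review medical charts of the patients admitted to UAMC following the same inclusion and exclusion criteria". It gives the period as 2008-2013 and intends the same variables as in the prospective cohort.

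The Sample Size Calculation section plans propensity matching on demographic, severity and laboratory variables. It also cites a trauma registry and a trauma surgeon group that did not change over the last 3 years. No section names who classifies SSI, or describes masking, adjudication or chart-abstraction rules.

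**The concern.** A comparison of infection rates is fair only if an infection of the same kind has the same chance of being counted in each cohort. Here the two cohorts reach the endpoint by different routes. A VeraFlo wound is inspected by people who know it received the technique under test, and it is cultured and photographed on a study schedule. A control wound contributes only what was written down in ordinary care years earlier.

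Two of the four superficial criteria are sensitive to this. Criterion d depends on whether a clinician chose to make the diagnosis. Criterion b depends on whether a culture was taken. Knowledge of the technique could make borderline wounds less likely to be called infected in the VeraFlo cohort. Closer observation and scheduled cultures could make them more likely to be called infected. Either could appear as a treatment effect or hide one. Matching balances who the patients are, not how their outcome was measured. The planned univariate, t-test and Kaplan-Meier analyses do not address it either.

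**Working it through.** The plan gives no figure for this point, so there is none to reproduce. The check sets the two cohorts side by side and then asks how much a small difference in ascertainment matters at this sample size.

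**Side by side**

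| | VeraFlo | Control |
|---|---|---|
| Source | Prospective study data | Chart review; a registry is also cited, but not said to hold CDC-defined SSI |
| Awareness | Treatment and study known | Ordinary care, no study in view |
| Cultures | Two fixed swabs per patient | No schedule given |
| Photographs | Listed as study data | None planned; they cannot be made in retrospect |
| Window | To the two-week clinic visit (Study Intervention and Duration) | Not stated; charts may run longer |
| Definition window | 30 days superficial, 30 or 90 days deep | Same on paper |

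**Weight of one call.** The sample size is 20, all VeraFlo. One patient is 1/20 = 5 percentage points. The plan's event-rate assumption is under 5%, with the arm not specified. An observed 1/20 has an exact 95% interval of 0.1% to 24.9%.

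**Effect on a test.** Assume 1:1 matching and 6/20 = 30% control events, which lies inside the 14-32% range in the Introduction. The plan states neither the ratio nor the control rate, and Fisher's exact test is my choice. Two-sided p-values:

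- 0/20 against 6/20: 2 × C(20,6)/C(40,6) = 2 × 38,760/3,838,380 = 0.020
- 1/20 against 6/20: 2 × [C(20,7) + 20 × C(20,6)]/C(40,7) = 2 × (77,520 + 775,200)/18,643,560 = 0.092
- 2/20 against 6/20: 0.235

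Under these assumptions, one judgement moves the result across 0.05.

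**Illustration of unequal detection.** Let observed rate = true rate × share detected. The shares are assumptions; the documents give none. Suppose there is no true effect and the true rate is the same in both cohorts.

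- Detection 70% VeraFlo, 90% control: at 14%, 9.8% against 12.6% (2.8 points); at 32%, 22.4% against 28.8% (6.4 points).
- Detection 50% VeraFlo, 90% control: at 14%, 7.0% against 12.6% (5.6 points, 1.1 events per 20); at 32%, 16.0% against 28.8% (12.8 points, 2.6 events per 20).
- Swapping the shares gives spurious harm of the same size. Equal shares give no difference.

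A true effect can also vanish. With true rates of 5% and 14%, full VeraFlo detection and 5/14 = 36% chart detection, both cohorts show 5%.

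**Illustration for criterion b.** If protocol swabs counted, and a share f of otherwise uninfected VeraFlo patients qualified through them, a true 5% would become 5% + 95% × f. That is 9.75% at f = 5%, 14.5% at f = 10% and 24% at f = 20%. This holds only if such swabs are treated as aseptically obtained cultures, which the protocol does not settle.

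**The case against.** The CDC definition is standard, and criterion d applies to both cohorts. The design is openly single-arm and historically controlled, so unmasked assessment comes with it. The protocol intends the same variables for both cohorts, describes follow-up as standard of care, and says wound culture is routine for contaminated wounds. The Data Collection Flow Sheet has no wound, swab, photograph or SSI row. The authors' stated confidence in the technique is a rationale for the study, not evidence of biased assessment.

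Much of this limits the point. A reader might infer that SSI in the VeraFlo cohort is judged by investigator-surgeons and control SSI by uninvolved clinicians. The documents do not support that. No SSI assessor is named, and the surgeon group is said to be unchanged for the last 3 years, so many control diagnoses were probably made by the same surgeons. Counted back from the planned first enrolment in September 2014, 3 years reach only to about September 2011, so the statement does not cover all of 2008-2013. The flow sheet also does not show daily wound surveillance; the documented extras are the photographs and the two fixed swabs.

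What does not stand is the idea that collecting the same variables solves the problem. It aligns the columns of the dataset, not how, when or with what knowledge the wounds were examined. The same surgeons diagnosing in routine care are also not in the same position as when they are testing a technique.

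**Conclusion.** The concern holds as a difference in data source, intensity of observation and awareness of the study between cohorts. It does not hold as a claim of wholly different assessors. It touches the primary outcome, and matching does not remove it.

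Two stronger readings should be resisted. One is that the bias favours VeraFlo: mechanisms run both ways, and the documents do not show which prevails. The other is that its size can be calculated from an assumed share of superficial SSIs diagnosed on judgement alone. No document gives that share, and applying it to the total SSI rate would ignore deep SSI, which has no criterion d.

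The one firm figure is that each reclassified VeraFlo patient is worth 5 points. The detection, criterion-b and p-value results rest on the assumptions stated with them. This should be settled before data are abstracted; it does not make the study unworkable.

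**What to change.** For the primary comparison, write one classification procedure for both cohorts:

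- Take SSI from the routine medical record (clinical and nursing notes, procedure notes, antibiotic orders, clinically ordered cultures) on a single form with the same CDC criteria.
- Fix one observation window, counted from surgery, and stop reading both cohorts' records at that day. If it is longer than the two-week visit, amend the follow-up statement. If it is two weeks, label the outcome accordingly, because the definitions run to 30 or 90 days.
- Use existing research staff who neither treated nor enrolled the patient, masked to cohort where the record allows. Research fellows may obtain consent, so this must be checked patient by patient.
- Do not count protocol-only swabs or study photographs towards SSI.
- Count criterion d only where a diagnosis is written in the clinical record.
- Repeat the comparison without criterion-d-only cases as a sensitivity analysis. State alongside it that criterion c requires an incision to be deliberately opened, which is hard to meet while a wet-to-dry control wound is still open. VeraFlo wounds are planned to be closed on day 4.

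The cost is protocol wording, one form and abstraction time; chart review and research staff are already planned. SSIs seen only through study observation leave the comparison, and the sensitivity analysis has fewer events. The treating clinician's note remains unmasked in the VeraFlo cohort, and that should be reported as a limitation.

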#### **Deep incisional SSI**

Must meet the following criteria:

Infection occurs within 30 or 90 days after the NHSN operative procedure (where day 1 = the procedure date)

*and*

involves deep soft tissues of the incision (e.g., fascial and muscle layers)

*and*

patient has at least one of the following:

- a. purulent drainage from the deep incision.
- b. a deep incision that spontaneously dehisces or is deliberately opened by a surgeon, attending physician\*\* or other designee and is culture-positive or not cultured

*and*

patient has at least one of the following signs or symptoms: fever ( $>38^{\circ}\text{C}$ ); localized pain or tenderness. A culture-negative finding does not meet this criterion.

- c. an abscess or other evidence of infection involving the deep incision that is detected on direct examination, during invasive procedure, or by histopathologic examination or imaging test.

#### **A. Secondary Efficacy Endpoint(s):**

1. Time to complete wound closure
2. Cost analysis: Cost-effectiveness ratio is determined by the net cost of material supplies, human labor, and the health effect of an intervention. The net cost includes the direct cost of drug, the equipment and their administration, and also on any savings that might be achieved by using this method, such as reduction in hospital stay, decrease of antibiotic usage.
3. Pain score as defined by the Wong-Baker Pain Scale related to the VeraFlo presence/manipulation.

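### The comfort hypothesis compares VeraFlo with wet-to-dry, but the only pain endpoint is specific to VeraFlo and no pain comparison is planned; time to closure also lacks a rule for reopened wounds

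*Combined protocol and SAP*

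**What the plan says.** **Pain.** The Clinical Hypotheses section expects the new technique to "increase patient comfort compared to the current common practice of wet-to-dry dressing changes". Item 3 of the Secondary Efficacy Endpoints is the only pain endpoint: "Pain score as defined by the Wong-Baker Pain Scale related to the VeraFlo presence/manipulation". The analysis paragraph under Sample Size Calculation names univariate analysis, a t-test and Kaplan-Meier, which "will be performed to compare rate of infection, time-to-closure, and cost analysis". Pain is not among these.

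Separately, Procedures Involved in the Human Research lists "wound closure details, pain level, cost" among the data to be collected, and Information Management repeats the item. For the historical cohort, the closing paragraph under Subject Exclusion Criteria says: "We will collect the same data points as in prospective cohort". The Data Collection Flow Sheet has no row for pain.

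**Closure.** Item 1 of the same endpoint list reads, in full, "Time to complete wound closure". In the VeraFlo cohort the device is used for three days, "followed by delayed primary closure on postoperative day 4". The data list includes closure details and "complications (if any) during their hospital stay and follow-up in clinic". Item c of the superficial SSI definition and item b of the deep SSI definition both include an incision that is deliberately opened; the deep definition adds spontaneous dehiscence.

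**The concern.** A hypothesis that one treatment is more comfortable than another needs a measure that both groups can have and a planned comparison of it. Here the endpoint is defined by the presence of a device that the controls never had, and the comparison list leaves pain out. The plan could report how VeraFlo patients tolerated the device, but not whether they were more comfortable than wet-to-dry patients. The Potential Benefits section also puts forward better patient comfort as a gain, so a reader of the results will expect evidence on it.

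For closure, the endpoint does not distinguish a wound that is closed and stays closed from one that is closed and later opened. The hypothesis of faster closure could then be judged on a time that ignores failed closures. If the rules for either endpoint are settled after the data are seen, they can be chosen to suit the result.

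**Working it through.** The plan states no figure for either endpoint, so there is none to reproduce.

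**Pain: the passages side by side**

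| Element | What the plan provides |
|---|---|
| Hypothesis | Comparative, against wet-to-dry |
| Endpoint | Wong-Baker score tied to VeraFlo; controls with a value as worded: none, by definition |
| Planned comparisons | Infection, time to closure, cost |
| Data item | General pain level, in both data lists; no scale, days or summary |
| Historical cohort | Same data points promised, from chart review |
| Flow sheet | No pain row |

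The first three rows do not connect. The data item and the promise for the historical cohort show that a common measure may be available, but nothing turns it into an endpoint or an analysis. No size can be computed, because the documents give no pain values or standard deviation.

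**Closure: could a reopened wound be scored as closed?** Take a VeraFlo patient closed on day 4 whose incision is later deliberately opened, is culture positive and is tender. Under item c of the superficial definition this is an SSI. Under the closure endpoint, nothing prevents the same patient from being recorded as closed on day 4. The reopening should be in the data, since closure details and complications are collected in hospital and in clinic. What is missing is the scoring rule.

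**Closure: size in the VeraFlo cohort only.** Inputs:
- Closure on day 4 in every patient, as scheduled in Procedures.
- A 14-day window, from the two-week visit in Study Intervention and Duration.
- Reopening proportion p between 2.6% (fascial dehiscence) and 9.8% (SSI), the Introduction's figures for delayed closure after trauma laparotomy. Using these as a stand-in for reopening is an assumption.
- No reopened wound re-closes within the window, so each contributes 14 days (also an assumption).

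Restricted mean time to sustained closure = (1 − p) × 4 + p × 14.
- p = 0.026: 0.974 × 4 + 0.026 × 14 = 3.896 + 0.364 = 4.26 days
- p = 0.098: 0.902 × 4 + 0.098 × 14 = 3.608 + 1.372 = 4.98 days

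The mean time to first closure is 4.0 days, so the shift is about 0.3 to 1.0 days. In patients this is 20 × 0.026 = 0.5 to 20 × 0.098 = 2.0 of the 20. If every reopened wound were instead re-closed on day 10 (assumption), (1 − p) × 4 + p × 10 gives 4.16 and 4.59 days. If no event reopens a wound, the shift is zero.

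The matching calculation for controls cannot be done: the documents give neither their closure times nor their reopening rate.

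**The case against.** On pain, the best reply is that item 3 is a device-tolerability measure, which is legitimate within one cohort, and that pain level is collected and promised for controls. Both points stand. A reader might infer that the study has no comparative pain data at all, and the documents do not support that. The narrower defect remains: a comparative hypothesis has no endpoint that both cohorts can have and no planned comparison. A field without scale, timing or analysis does not fill that gap.

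On closure, three replies carry weight. First, closure on day 4 is part of the treatment under test, so an early closure day is the intended effect and not an artefact. Second, infected wounds that are opened are still caught by the primary outcome. Third, a reader might infer that the two cohorts share no closure event, because the Introduction describes several ways of managing a wound after wet-to-dry dressings. That goes too far: complete closure can apply to any of these routes, and only an operational definition is missing. A reader might also infer that the comparison is biased in favour of VeraFlo. The documents do not show this, because closures in controls can fail too and are equally unscored.

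What remains is that a closed and then reopened wound has no stated score in either cohort.

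**Conclusion.** The pain point holds. As written, the plan cannot answer its own comfort hypothesis, although the data it intends to collect may allow it to. No magnitude can be attached.

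The closure point holds as a secondary matter of definition. The size and direction of its effect on the comparison are unknown. For VeraFlo alone the mean would move from 4.0 to about 4.3 to 5.0 days. That rests on the delayed-closure dehiscence and SSI rates standing in for reopening, closure on day 4 in every patient, and no re-closure within 14 days. It is an illustration and not a strict bound, since wounds may also reopen for other reasons.

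Both endpoints are secondary. The changes should be made, but neither gap undermines the primary outcome.

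**What to change.** **Pain.**
- Make general pain level the comparative endpoint, abstracted the same way over the same prespecified in-hospital postoperative days in both cohorts, with the scale and summary measure stated.
- Add it to the comparisons in the Statistical Analysis section and to the flow sheet.
- Report by cohort and day how many patients have a score, because discharge times may differ.
- Keep the VeraFlo-specific Wong-Baker score as a descriptive measure of tolerability.
- Check first that the historical charts hold usable scores on a comparable scale; the documents do not show that they do. If they do not, report pain descriptively and remove the comparative comfort claim from Clinical Hypotheses.

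**Closure.**
- In both cohorts, measure from the date of the index operation to the first day with no open skin wound that then stays closed through a fixed postoperative day.
- Choose that day so that wound status is available in both cohorts. The two-week visit is stated for study subjects, and its presence in historical charts needs checking.
- Count a reopened wound as not closed until it is re-closed.
- State in advance how death and loss to follow-up are handled, and report first closure descriptively.

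**Cost.** A few sentences of definition and some extra chart abstraction for pain scores and reopening and re-closure dates. General postoperative pain is less specific to the dressing than the present item, the comfort claim may end up descriptive only, and the VeraFlo closure time may look less favourable. Reopenings after the chosen day will not be captured.
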